The expected duration of the participant's participation	The screening period from signing the informed consent form to enrollment is expected to be 4 weeks, the treatment period is 1~8 weeks, and the follow-up after the last treatment are divided into short-term follow-up and long-term follow-up, and the maximum duration of expected participation of each subject from screening to the end of short-term follow-up is 12 weeks +3 months. Long-term follow-up continued after the end of the short-term follow-up until the fifth year after the end of the last radiotherapy. (After a 3-month follow-up after the last treatment, a "Medical Device Clinical Trial Report" will be issued for the registration of this trial

product Declaration.)

Expected overall duration of clinical trials and long-term follow-up	
The first subject is expected to be enrolled in June 2024, and the clinical trial institution expects to enroll 12 subjects per month, for a total enrollment time of about 4 months, and the last subject ends the trial (short-term follow-up) is In April 2025.
 
The last subject to end long-term follow-up in January 2030.

Primary effectiveness	
Disease Control Rate (DCR).
 
Evaluation time: 3 months \pm 7 days after the last treatment.
 
Definition of indicators: Complete Response (CR), Partial Response (PR), Stable Disease (SD) for disease control. Proportion of participants who developed disease control three months after the end of the last radiotherapy.

Evaluation indicators	
Evaluation methodology: Response Evaluation Criteria in Solid Tumors RECIST Version 1.1 (RECIST 1.1) by an independent imaging review team in tumour CT or MRI imaging before and after treatment were assessed.
 
Participants who discontinued the trial for any reason (except loss to follow-up) before the end of radiation therapy were considered to have not controlled.

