Evaluation method: The changes in tumor CT or MRI imaging before and after treatment were evaluated by an independent imaging review panel according to RECIST 1.1. At 3 months of radiographic evaluation, if PD is found, PET-CT is required to confirm it.

Calculation formula: DCR = number of disease control subjects / total number of subjects \times 100%.

Criteria: See RECIST 1.1 for details. At the time of 3-month imaging evaluation, if the patient is found to have PD, PET-CT examination is required to confirm it, if progress is confirmed, it is recorded as PD, if progress cannot be confirmed, it may

be false progression, and it is recorded as SD. If prostate cancer does not have biochemical recurrence, PET-CT examination is not required, and there is no metastasis by default, which is regarded as tumor control, and if biochemical recurrence occurs, it is regarded as tumor not controlled, and PET-CT is required to confirm tumor metastasis.

Note: Participants who aborted the trial for any reason (except loss to follow-up) before the end of the last radiation therapy were considered to have disease progression (PD) or were not controlled. Disease site evaluation uses the same approach as baseline, including consistent contrasted/non-contrast scans and prompt scanning. If changes are needed, the case must be discussed with a radiologist to determine whether an alternative approach is possible. If not, the objective situation in the future is unclear.

3.1.4.2 Secondary effectiveness evaluation indicators and their methods and timing of evaluation, recording, analysis

(1) Objective response rate (ORR).

Reason for selection: The Guidelines for the Review of Clinical Evaluation Technologies of Proton Carbon Ion Therapy Systems (CFDA Circular No. 4 [2018]) recommends the use of the latest version of the commonly used evaluation criteria for radiation oncology as the clinical trial evaluation criteria, so RECIST 1.1 is used. Relevant indicators as effectiveness evaluation criteria; Due to the particularity of the disease, the evaluation method recommended in the relevant diagnosis and treatment guidelines is selected. All of them can directly measure the effect of radiotherapy and are widely recognized and applied by clinicians.

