Definition of indicators: CR or PR after the end of treatment is considered objective remission, prostate cancer has no biochemical recurrence at the end of the last treatment, and no regional lymph nodes or distant metastasis are considered objective remission. Proportion of participants who experienced objective remission at each time point after the end of the last treatment.

Metric type: Qualitative.

Data collection time: screen period, 3 days, 1 month \pm 7 days, 2 months, \pm 7 days, 3 months, \pm 7 days after the end of the last treatment.

Evaluation time: 3 days, 1 month \pm 7 days, 2 months, \pm 7 days, 3 months, \pm 7 days after the last treatment.

Site of evaluation: Tumor receiving radiation therapy.

Evaluation method: The changes in tumor CT or MRI imaging before and after treatment were evaluated by an independent imaging review panel according to RECIST 1.1. At 3 months of radiographic evaluation, if PD is found, PET-CT is required to confirm it.

Calculation formula: ORR = number of subjects in objective response / total number of subjects \times 100%.

Criteria: See RECIST 1.1 for details. At the time of 3-month imaging evaluation, if the patient is found to have PD, PET-CT examination is required to confirm it, if progress is confirmed, it is recorded as PD, if progress cannot be confirmed, it may be false progression, and it is recorded as SD. If prostate cancer does not have biochemical recurrence, PET-CT examination is not required, and there is no metastasis by default, which is regarded as objective remission, and if biochemical recurrence occurs, it is regarded as not objectively remission, and PET-CT is required to confirm tumor metastasis.

Note: Participants who aborted the trial for any reason (other than loss to follow-up) before the end of the last radiotherapy were considered to have not responded objectively. Disease site evaluation uses the same approach as baseline, including consistent contrasted/non-contrast scans and prompt scanning. If changes are needed, the case must be discussed with a radiologist to determine whether an alternative approach is possible. If not, the objective situation in the future is unclear.

(2) Tumor disease control rate (DCR).

Reason for selection: DCR 3 months after the end of the last treatment was the primary evaluation index, and DCR at other follow-up time was used as a secondary evaluation index.

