4.9 Selection criteria and rationale for participants included in the analysis

Full Analysis Set (FAS): All subjects who received at least 1 investigational device treatment and at least one post-baseline observation data will be enrolled in FAS, according to the basic principles of intention-to-treat analysis. FAS will be used as the primary population for baseline data and sensitivity analysis for validity evaluation. Participants may only be excluded in very limited circumstances, including when important inclusion criteria are violated and no observational data are available after enrollment.

Compliant protocol set (PPS): is a subset of FAS, defined as subjects who have measurable lesions at baseline and have completed at least one assessment of primary efficacy indicators after baseline. PPS will be the primary population for the effectiveness evaluation of this study.

Safety dataset (SS): all participants who received at least 1 study device treatment and at least one safety assessment. SS will be the primary population for safety analysis in this study.

The assessment of baseline characteristics will use the full set of analyses; The evaluation of effectiveness will use both the full analysis set and the conforming protocol set; Security analysis uses security datasets.

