2.1 Effectiveness evaluation indicators

2.1.1 Key Effectiveness Indicators

- **Tumor disease control rate (DCR) at 3 months after the end of last treatment**

The occurrence of CR, PR and SD after the end of treatment was considered to be disease control, and the absence of biochemical recurrence at the end of treatment of prostate cancer was considered to be disease control. Proportion of subjects with disease control 3 months after the end of the last radiation therapy.

Calculation formula: $DCR = \text{number of subjects under disease control} / \text{total number of subjects} \times 100\%$

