Full Analysis Set (FAS): According to the basic principles of intention-to-treat analysis, all participants who received at least one treatment with an investigational device and at least one post-baseline observational data will be included in the FAS. FAS will be used as the main population for the baseline data and effectiveness evaluation sensitivity analysis of this study. Exclusion is only possible in very limited circumstances, including cases where important enrollment criteria have been violated and no observational data have been available after enrollment.

Per-Protocol Set (PPS): is a subset of FAS and refers to subjects with measurable lesions at baseline who have completed at least one primary efficacy measure assessment after baseline. PPS will be the main population in the evaluation of the effectiveness of this study.

Safety Set (SS): All participants who received at least one treatment with an investigational device and had at least one safety evaluation. SS will be the primary population for safety analysis in this study.

The baseline characteristics will be assessed using the full analysis set, the effectiveness will be assessed using both the full analysis set and the conformance set, and the safety analysis will use the safety dataset.

4 data processing

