5.6 Sensitivity analysis

If the receiver effectiveness index was filled by the worst observational data carry-over (WOCF) method, the sensitivity analysis of the main effectiveness measure was performed based on FAS. When the conclusions of FAS and PPS are consistent, the confidence of the test results can be enhanced. When the conclusions of the two groups are inconsistent, the analysis based on the inclusion of PPS population should be the main one, and the differences should be fully discussed and explained.

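### PPS decides the primary DCR result, but as worded it can leave out early stoppers whom the Protocol scores as not controlled, and the SAP gives two conflicting fill rules for the FAS check

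*SAP*

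**What the plan says.** **Which population decides.** Protocol 4.9 states "PPS will be the primary population for the effectiveness evaluation of this study", and SAP 3 agrees. SAP 5.4.1 reports the primary endpoint in both FAS and PPS. SAP 5.6 adds the precedence rule for a disagreement: "the analysis based on the inclusion of PPS population should be the main one, and the differences should be fully discussed and explained".

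**Who is in each set.** SAP 3 defines PPS as "subjects with measurable lesions at baseline who have completed at least one primary efficacy measure assessment after baseline". FAS needs at least one device treatment and "at least one post-baseline observational data will be included in the FAS". Protocol 4.9 defines both in the same way.

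**What counts as a failure.** The Protocol summary says "Participants who discontinued the trial for any reason (except loss to follow-up) before the end of radiation therapy were considered to have not controlled". The note in Protocol 3.1.4.1 repeats it: "Participants who aborted the trial for any reason (except loss to follow-up) before the end of the last radiation therapy were considered" progressed or not controlled. SAP 2.1.1 defines the endpoint only as "Proportion of subjects with disease control 3 months after the end of the last radiation therapy". Neither it nor SAP 5.4.1 carries the early-stopper rule.

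**Missing month-3 values.**

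| Place | Rule for the primary indicator |
|---|---|
| Protocol 4.7.2(3) | worst case may be used |
| SAP 4.3, PPS | no filling needed |
| SAP 4.3, FAS sensitivity analysis | not filled |
| SAP 5.4.1, FAS sensitivity analysis | filled by WOCF |
| SAP 4.1 | presumes a WOCF analysis |
| SAP 5.6 | mentions WOCF conditionally |

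The SAP abbreviation list expands WOCF as worst observation carried forward.

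**The concern.** A patient who stops radiotherapy early and never has a month-3 scan is a failure under the Protocol's endpoint definition, but has no completed assessment of the kind PPS asks for. If that patient is left out, the deciding analysis drops a failure from both the count and the denominator, and the reported DCR rises. In a single-arm comparison with a fixed 80% target, no control arm offsets this.

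The FAS analysis is where the difference should show. With no fill, the patient may again go uncounted. With WOCF, a stable-disease reading at an early visit is carried forward as controlled, and a patient with no post-treatment scan has nothing to carry. A very early stopper with no post-baseline data can also fall outside FAS. SAP 5.6 asks for any disagreement to be discussed, but that does not change which result prevails.

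**Working it through.** **Step 1: reproduce the plan's sample size.** Inputs (Protocol summary, 4.2 to 4.4): target 0.80, expected 0.95, two-sided alpha 0.05, power 80%, dropout 10%.

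n = [1.960·√(0.80·0.20) + 0.842·√(0.95·0.05)]² / 0.15² = 41.6, so 42; 42/0.9 = 46.7, so 47. Both figures match the plan.

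**Step 2: the success boundary.** Protocol 4.5 and SAP 5.4.1 require the lower limit of the two-sided 95% Clopper-Pearson interval to exceed 80%.

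| n | Fewest controlled to pass | Failures allowed | Lower limit |
|---|---|---|---|
| 41 | 38 | 3 | 80.1% |
| 42 | 39 | 3 | 80.5% |
| 43 | 40 | 3 | 80.9% |
| 44 | 41 | 3 | 81.3% |
| 45 | 42 | 3 | 81.7% |
| 46 | 43 | 3 | 82.1% |
| 47 | 44 | 3 | 82.5% |

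Removing failures from the denominator costs nothing on this scale. With 47 treated and 4 failures, one of them an unscanned early stopper, PPS gives 43/46, lower limit 82.1%, a pass. The Protocol's rule gives 43/47, lower limit 79.6%, a fail. This needs no assumption about rates.

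**Step 3: early stoppers.** The documents give no early-stopping rate. Assume s of 47 stop early unscanned, and that true control with them counted as failures is exactly 80%. Control among the others is then 0.80·47/(47 − s).

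- PPS without them passes with probability P(at most 3 failures among 47 − s).
- With them counted, the probability is P(at most 3 − s failures among 47 − s).

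| s | Control among the others | PPS passes, stoppers omitted | Passes, stoppers counted |
|---|---|---|---|
| 0 | 0.800 | 0.9% | 0.9% |
| 1 | 0.817 | 2.2% | 0.6% |
| 2 | 0.836 | 4.8% | 0.3% |
| 3 | 0.855 | 10.0% | 0.1% |

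The nominal one-sided level is 2.5%.

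**Step 4: all patients without a month-3 result.** Let u be the unassessed share and g the share of those who are uncontrolled (both my assumptions), with true control 80%. Control among the assessed is (0.80 − u(1 − g))/(1 − u), and the PPS pass probability is averaged over n ~ Bin(47, 1 − u).

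| u | g = 0.2 (unrelated to outcome) | g = 0.5 | g = 1 |
|---|---|---|---|
| 5% | 1.4% | 2.5% | 6.3% |
| 10% | 1.7% | 5.3% | 26.2% |

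At u = 2%, even g = 1 gives only 2.1%. The 2.5% level is passed when g exceeds about 0.30 at u = 10%, or about 0.50 at u = 5%.

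**Step 5: tipping point.** With 47 treated, 4 failures in total fail the rule. With f failures observed in PPS (f = 0 to 3), 4 − f failures among the unassessed would reverse a PPS pass.

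**The case against.** **PPS primacy is a Protocol choice.** A reader might infer that the SAP departs from the Protocol by letting PPS decide. It does not: Protocol 4.9 makes PPS primary, and this fits a sample size built on 42 patients with month-3 data. The SAP adds only the precedence sentence. This objection stands, and I do not ask for PPS to be displaced.

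**Exclusion is not stated.** The Protocol assigns early stoppers a category, the DCR formula divides by the total number of subjects, and the SAP says it was developed from the Protocol, so silence need not repeal the rule. At least one assessment might also include DCR at the earlier visits, and SAP 5.3.2 settles set membership before database lock. These points make the text ambiguous. They do not resolve it: Protocol 3.1.4.2 says "DCR 3 months after the end of the last treatment was the primary evaluation index" and makes the earlier visits secondary, and nothing says that an assigned failure counts as an assessment.

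**WOCF is not a breach.** Protocol 4.7.2(3) permits the worst case and does not require it, so the stronger claim that the SAP violates the Protocol fails. The contradiction between SAP 4.3 and 5.4.1 remains.

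**The 26.2% figure is a stress case.** It needs 10% unassessed, all uncontrolled, with true control exactly 80%. The 10% in Protocol 4.4 also covers other deviations. It should not be read as the trial's error rate.

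**A stricter safeguard is tempting.** One could bar an unqualified claim whenever 4 − f does not exceed the number missing, m. But 4 − f ≤ m is the same as f + m ≥ 4, which is the all-treated worst-case test failing. At 95% control among the assessed, the chance of an unqualified claim would be 79%, 32% or 8% at 0%, 5% or 10% missing, and zero once 4 are missing. The design allows for 47 − 42 = 5, so I do not propose that rule.

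**Conclusion.** The point holds in this form. PPS decides. On the natural reading, its wording can omit unscanned early stoppers whom the Protocol scores as failures. The SAP also contradicts itself on how the FAS check treats missing primary values. This should be fixed before database lock.

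The exact part of the size is that one omitted failure can turn a fail into a pass (43/47 against 43/46). The false-pass rates of 2.2%, 4.8% and 10.0% rest on my assumption of 1, 2 or 3 unscanned early stoppers, with true control at 80%. For other missing patients the effect depends on why they are missing. If missingness is unrelated to outcome, the false-pass rate is 1.4% to 1.7% at 5% to 10% unassessed, below the nominal 2.5%. The documents therefore do not support saying that the PPS analysis is biased whatever the reason for missing data, or that these patients are certain to be excluded.

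**What to change.** 1. Copy the not-controlled rule of Protocol 3.1.4.1 into SAP 2.1.1. State in Protocol 4.9 and SAP 3 that these patients are in PPS and FAS as failures, whether or not scanned. Suggested wording for PPS: the qualifying assessment is the month-3 assessment or an assigned month-3 failure.
2. Reconcile SAP 4.3 with 4.1, 5.4.1 and 5.6, so that one rule governs the FAS sensitivity analysis: missing month-3 DCR is counted as not controlled, as Protocol 4.7.2(3) permits, in place of no fill or WOCF.
3. Beside PPS, report as supportive information only the all-treated worst-case result and the tipping number 4 − f. PPS, corrected as in item 1, stays the deciding analysis.

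**Cost.** Wording in both documents and one small table, with no change to sample size or conduct. The reported DCR may be lower and a pass harder, because each Protocol-defined early stopper uses one of the three allowed failures. If the other patients are controlled at 95%, the chance of a pass is 79% with no such stopper, 59% with one, 34% with two and 10% with three. If the planned 95% already counts early stoppers as failures, as the Protocol's definition implies, the correction only applies the endpoint as planned.

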5.7 Subgroup analysis

Subgroup analyses were performed for primary effectiveness measures, including but not limited to:

(1) Tumor site (tumors of the nervous system, head and neck, chest, abdomen, spine, pelvis, limbs, etc.);

The number and percentage of local control of tumors under the planned visits of each subgroup were summarized.

5.8 Interim analysis

Not applicable.

6 Annex

Appendix 1 Flowchart of Subject Distribution

[figure not shown]

Fig.1 Sample flow chart of subject distribution
